Participant recruitment is based on the Arm of the PCP the child is scheduled with for the upcoming WCV or completed WCV. Participant assignment follows PCPs random assignment at the point of scheduling and initial recruitment. The study team expects that most of the participants will see the PCP that they are originally scheduled with or a PCP in the same Arm. However, the study team anticipates that participants will be lost when the child does not receive allocated treatment (i.e., child's WCV is conducted by a PCP in different Arm than scheduled) due to absences or unplanned events. Loss of these participants is accounted for in the sample size for per protocol analyses. However, the primary BMI outcome analysis is an intent- to-treat analyses and will include these children, regardless of the PCP's Arm at the point of care (WCV).

Participants will be reminded to complete study consent, questionnaires, study measures, health coach calls, and grocery store tour via follow-up phone calls, emails, MyGeisinger patient portal, and text messages sent utilizing the internal Geisinger process that is currently leveraged to send appointment reminders to patients. This is an approved platform by ISO.

All data (EHR and patient-self report) will be kept behind the Geisinger firewall on password-protected servers that are only accessible to Geisinger IRB-approved staff. For data shared with PSU, all Geisinger IT/ISO policies regarding secure transportation of patient data will be followed. Data shared outside Geisinger will be stored in a secure location to ensure patient data is protected.

Participant Compensation

Parents/guardian participants will receive a \$50 check per survey completion at baseline, 6 months, and 12 months for a total of \$150, if the patient completes all 3 surveys, they will receive an additional \$50 for a total of up to \$200. Geisinger providers will not be compensated for completion of study questionnaires. Participating clinics will receive a stipend of \$500-\$1,000 depending on number of qualifying PCPs as those with a higher number may experience greater disruption to workflow with added burden of collecting patient-reported data. Note that all clinics now collect patient-reported data with varied workflows and technology resources (e.g., tablets, kiosks) and this burden is expected to be minimal.

Participant Withdrawal

Participants who choose to withdraw from the study will not be contacted for further survey data collection. In addition, for participants in Arm 3, if the choice is made to withdraw, they will not receive any further contact from their health coach. Participants may be withdrawn from the study by an investigator if they choose to switch providers or leave Geisinger. All data collected up to the point of withdrawal may be used for analysis purposes.

Data Management Procedures and Confidentiality

Data collected as part of this study will be kept indefinitely for future analysis such as potential follow-up analysis to determine long-term study impacts, and for use in grant planning to pursue additional research-related activities. These data will be stored on stored locally on Geisinger encrypted, password-protected servers behind the Geisinger firewall. Only trained study personnel who adhere to the National Institutes of Health (NIH) policies on the protection

of human subject participants in research, and are approved by the Geisinger IRB, will have access to study data.

Questionnaires will be administered using REDCap, which will also be used to manage and store related data elements (e.g., participant tracking). Data from paper versions of self-administered questionnaires will be manually entered into an electronic dataset. Double-entry and verification steps will be taken to reduce potential for human error. Electronic questionnaire data will be stored internally on Geisinger's secured network and access to REDCap will be restricted to approved study personnel. Study participant information will not be released to any party without the participant's permission. RedCap access occurs over password-protected channels only accessible via the use of an authenticator. Data is stored locally on Geisinger encrypted, password-protected servers behind the Geisinger firewall.

In the event that data would be transferred outside of Geisinger, it would be done using a secure file transport system maintained by Geisinger IT/ISO. This secure transport method would allow access only to approved IRB study staff with unique usernames and passwords required to access the site.

Data Analysis/ Statistical Considerations

Table 2. Estimated Sample Size per Randomization Arm

Effect size*	# Physicians per group	# participants per Physician	Total N per group
0.20	20	32	640
0.20	25	25	625
0.25	20	19	380
0.25	25	15	375

*Cohen's d: mean difference / SD

Sample Size and Power

Our preliminary data comparing the change in BMIz between WCV vs. **PRO WCV** yielded a difference of 0.05 units.⁶ This corresponded to an effect size (Cohen's d) of approximately 0.20 of a standard deviation. Additionally, based on our preliminary data and the literature, we estimate the intra-cluster correlation (ICC) to be 0.005 to account for the clustering of participant families within PCP. We recognize that participants may be lost to follow up during the course of the study or that we will not recruit equal number of participant families across all PCPs. Therefore, our sample size calculations further assume a coefficient of variation (COV) equal to 0.25 to account for this potential imbalance. This parameter being greater than 0 (i.e., equal sample size across clusters) increases the required sample size. Lastly, to account for two *a priori* statistical comparisons in Aim 1 (**WCV vs PRO WCV**, **WCV vs. PRO WCV + Food Care**), the significance level is set at 2.5%. **Table 2** reports the required sample size for enrollment under the stated assumptions. All calculations assume 80% power and an overall significance level of 5% such that each of the two comparisons will be made at the 2.5% significance level.

The software PASS v15 was used for all calculations, specifically the module for cluster randomized trials for two means. Table 2 reports the required sample size for enrollment under the above stated assumptions (reproduced in this response). We also varied the effect size to additionally include 0.25 and using 20 and 25 PCPs per arm to understand how varying-the

parameters affected the sample sizes. For example, assuming an effect size of 0.20, ICC of 0.005, COV of 0.25, 80% power, and 0.025 significance level, the study would be required to enroll 28 participant families per PCP per arm for a total of 560 families per arm. However, we further inflated the sample size to account for 7% of participants not receiving allocated treatment (i.e., WCV completed by a PCP in a different Arm than scheduled) and a 10% dropout at 1 year. This yields a sample size of 675 per arm or, with rounding, 33 families per each of 20 PCPs, for a total of 675 per arm (N=2,025 across all three arms).

The study will have 80% power to detect an effect size of 0.20 with 20 PCPs per randomization arm and 33 participant families per PCP, for a total of 2,025 across all three groups in Aim 1. If we are able to obtain more PCPs, then we can reduce the number of families. Also, if the effect size is larger than we observed in our preliminary work,⁶ then the study will have > 80%. It is recognized that to assess for mediation and moderation that a larger sample size is required and thus, we do not expect to have a large power to detect these effects. Thus, Aim 2 results will be descriptive in nature. Given that multiple recruitment strategies are simultaneously in place, and the rate of enrollment is about 10 participants/week when 95% of the targeted sample has been achieved, the study has a buffer of 15 additional participants who may be in latter stages of recruitment when the sample is achieved. In other words, up to 2040 participants may be enrolled.

Outcomes

The primary child-level outcome is the 1-year difference in change in BMIz between study arms using World Health Organization growth reference standards. BMI values will be obtained from Geisinger clinical care visits, documented in the EHR. Values obtained at well child visits (preferred), clinical visits, or self-report during the study period, ideally 12 months, 1 day apart will be utilized but values from baseline WCV to 9 to 18 month follow-up may be used to assess the primary outcome. This primary outcome is chosen because it reflects the difference in the effectiveness of each intervention versus standard of care in preventing obesity among a high-risk population of preschool-aged children. The difference in the difference between groups is chosen because the intervention is randomized at the PCP and not the patient-level. Parent self-report of child weight and height is added to supplement primary outcome data given unprecedented changes in pediatric care secondary to the pandemic. Specifically, the availability of WCVs has decreased due to staff turnovers yet the demand has decreased as families delay or forgo preventive care. To optimize follow-up height and weight data collection, parents of children without a clinical BMI at about 1-year post-baseline WCV, will be encouraged to complete the child's follow-up WCV, per clinical schedule, or to visit the clinic for height and weight measures. Among this subset of the study population (implemented in September 2022), parent self-reported data about child's height and weight will be collected before the WCV or clinic visit.¹⁵³⁻¹⁵⁶ Parents will be asked whether the self-reported data are estimates or measured at home.¹⁵³⁻¹⁵⁶ Among a smaller subset, the self-reported data will be compared with objective height and weight collected in usual clinical care. Concordance between the parent self-report and clinical measures will be evaluated for validation of self-reported data. If the variation among self-report with objective clinical measures is acceptable, self-reported data may be used as follow-up measures. To determine if the variation is acceptable, variation will be compared to the literature to inform analytical strategies for using supplemental parent-reported data in the absence of clinical measures.¹⁵³⁻¹⁵⁶ The use of self-reported measures is anticipated for studies

conducted during the pandemic and will likely be found in emerging and current literature.¹⁵⁷ While many adiposity outcomes could be used, this outcome will facilitate interpretation of the relevance of the findings among PCPs, health care administrators, policy makers, and researchers who pursue future systematic reviews of delivery care models to prevent childhood obesity. Nonetheless, BMIz can be too restrictive to evaluate success and may not be meaningful to parents or clinicians.¹²² Therefore, we will also evaluate the proportion of children overweight and obese at 1-year follow-up per CDC guidance and definitions (<https://www.cdc.gov/obesity/childhood/defining.html>), difference in raw BMI and difference in BMI50 between study arms, and BMIz extended.¹⁵⁸⁻¹⁶⁰ Patient stakeholders to the project (Patient Advisory Council on Obesity, PACO) identified meaningful secondary outcomes and PCP's identified mediating pathways to inform steps that parents and PCPs can take together to prevent obesity. Specifically, findings will help to inform parents of what they can realistically expect for their children if they pursue standard of care WCV, complete the PRO risk assessment and engage in discussion with their child's PCP, or take these steps and participate in a community-based nutrition program. PCPs would understand benefit of utilizing FNPA, training, and intentionally engaging parents in counseling on childhood obesity prevention.

Analytic Plan

During the start-up of the study we will develop a formal Data Management Plan to document how data will be collected, organized, stored, as well as a statistical analysis plan. Descriptive statistics will include evaluation of all data for underlying distribution and summary statistics, using means with standard deviations and medians with interquartile range for continuous variables, and frequency with percentages for categorical variables. The data will be summarized for all patients enrolled and will be stratified by randomization arm and study time point. We will assess the quality of data, evaluating outliers and patterns of missing data using graphs such as histograms and stem-and-leaf plots. Bi-variate analyses will be used to assess differences in patients (e.g., parent BMI, child biological sex, baseline BMI) between randomization arms. Since it is not recommended to perform inferential statistics to assess balance of baseline participant, family, community, and physician factors in a randomized study, we will use standardized differences.¹⁰³ Any standardized difference > 0.10 will be considered unbalanced and, thus, a potential confounding variable. We will also follow the CONSORT¹⁰⁴ extension to cluster randomized trials when reporting results.

As data is collected from participants as part of this research study, in an effort to facilitate additional analyses, the Geisinger study team plans to share a de-identified data set with PSU. This data set will be shared utilizing Geisinger IT-approved methodologies (Secure Transport, e-secure, etc.) to ensure that patient data is protected. These data will be stored at PSU in a secure network location that is only accessible to PSU study staff. These analyses will assist in exploring additional study research questions that may arise.

Aim 1. The primary outcome variable is change in BMIz at 12 months. BMIz is the most widely used obesity-related outcome per systematic review and thus was chosen for comparability with prior literature.^{11,105} The primary analysis will follow the “intention-to-treat” principal. That is, all participants enrolled will be analyzed according to their group assignment at the point of care (WCV) regardless of intervention received and compliance. Analyses will

take into account the clustered nature of the study design. To test the Aim 1 hypothesis that participants will have a lower change in BMIz (and secondarily, changes in BMI, BMI50, BMIz extended) in Arms 2 and 3, as compared to Arm 1, mixed linear models^{106,107} with restricted maximum likelihood estimation will be fit. The models will include a random effect for PCPs and will be assumed to follow a Gaussian distribution. These analyses will adjust for the stratification factors used in the randomization scheme and any baseline variables found to vary across intervention arms as identified above. Contrast statements will be written as functions of the estimated regression coefficients to estimate the effect of the interventions compared to standard WCV using a two-sided alpha of 0.025 to account for multiple testing. Model assumptions will be examined (e.g., QQ plots to assess normally distributed residuals) and of the underlying Gaussian random effect distribution. Secondary analyses will estimate the effectiveness of the interventions on the percent of children overweight and obese (≥ 85 percentile of BMI and ≥ 95 percentile of BMI) at 12 months. A similar strategy will be employed using a generalized linear mixed model assuming a binomial distribution for the outcomes. These models will treat the binary outcomes as measured from the 12-month visit. Analysis of secondary outcomes in Aims 1b and 1c (involvement in preventive care, parent and home factors) will follow the same strategy as described above. Due to lagging enrollment, the study modified data collection for secondary outcome in specific aim 1b- involvement in preventive care- just after 50% enrollment was reached. The timing of this outcome measure was changed from pre-visit only to pre- or -post visit to allow for families to enroll and complete baseline data collection after a completed WCV. As there are complementary analysis methods for cluster randomized trials, we will also fit Bayesian random effect models¹⁰⁸⁻¹¹⁰ for continuous and binary outcomes. Each model will use an inverse gamma prior for the cluster random effect variance parameter.¹¹¹ We will note any differences in the effect estimates across methods.

Aim 2. The primary outcome variable is the same as in Aim 1, change in BMIz at 12 months. Aim 2 involves the assessment of mediating and moderating effects of PCP, parental and child behaviors (see list of variables in **Appendix B**). For a variable to be considered a mediator it must be associated with and in the casual pathway between the intervention and outcome. Therefore, we will first fit mixed linear models to each hypothesized mediator as dependent variables following the approach described in Aim 1. We will then fit similar models with BMIz as the outcome and each potential mediator as independent variable. Any variable found to be associated with intervention and BMIz will be considered a potential mediator variable. Our list of candidate mediator variables is measured at both the subject (parent and child) and cluster levels (PCP). To appropriately fit models with mediation at different levels we will rewrite the mixed models of Aim 1 as multilevel structure equation models (MSEM)¹¹² to include the variables in the analysis. Results will be expressed as total, direct, and indirect effects as estimated from the model. Moderation will be assessed using the MSEM framework.¹¹³ In Aim 1, we will also fit complementary Bayesian models to assess robustness of effect estimates. Aim 2 outcomes may be evaluated using secondary outcomes including raw BMI, BMI50, and BMIz extended.

Missing Data Considerations. We will minimize missing data by querying the EHR for anticipated and scheduled 1-year follow-up WCVs, sending reminders to each participant to schedule and attend appointment, and reminding participants of 1-year follow-up study questionnaires. Missing data, however, are inevitable in a longitudinal study due to dropout and

nonresponse to study questionnaire items. We anticipate that no more than 7% of randomized subjects will not receive allocated treatment and 10% of randomized subjects will fail to complete the study;^{63,90,115} but reasons for loss at point of WCV care and dropout will be documented. Before proceeding with primary analyses, we will characterize patterns of missingness using exploratory analyses to provide insights into how to handle the missing data. Participants with missing data will be compared to participants with complete data to ensure there are no differences. Depending on the amount of missing data, we will use a non-parametric missing data imputation method based on random forests.¹¹⁶ This method has been shown to perform as well as or better than more traditional methods of imputation, and it has the advantage of imputing both continuous and categorical data. By using random forests, we can capture non-linear relationships and interactions present in the dataset that may otherwise be missed when using a different method. At least 5 complete datasets will be created and combined using the methods of Rubin.¹¹⁷

Heterogeneity of treatment effect (HTE). HTE analyses are incorporated into Aim 2 when examining moderator effects. Additional sub-group analyses will be performed by child sex (males, females) and baseline BMI weight category (overweight, obese). These sub-group analyses will employ the same models as described in Aim 2.

Aim 3. The **RE-AIM framework**²⁹ will be used to evaluate the interventions' reach to the target population and subgroups (e.g., by provider type, those with food insecurity and hunger), comparative effectiveness, adoption by PCPs, implementation fidelity and barriers, and maintenance of intervention components over time, so as to inform translation of this study into practice.

EXPECTED RISKS/ BENEFITS

Potential Risks

The greatest potential risk to participants in this research is a loss of confidentiality. To minimize the risk of loss of confidentiality, all data collected as part of this study will be stored on the Geisinger password-protected network only accessible to IRB-approved study staff. Participants will also be assigned a unique study ID for data collection. In the event that any data would be shared outside of Geisinger, it would be done using an IT-approved secure transport method to ensure data security is maintained.

Benefits

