Trained study team dietitians may function in the role of the Health Coach in the event of staff shortages; otherwise, the dietitians have no other role on the project. For the purpose of implementation evaluation, Health Coach will be asked to complete questionnaires at baseline, 12- and 24-month follow-up periods. The grocery store tour will be delivered by trained, in-store nutritionists across the study region (e.g., Giant Foods, Wegmans, Weis Markets). Grocery store tours are usual practice for in-store nutritionists. To ensure participants are able to receive the grocery store tour trainings, they will be offered both in-person and virtually (utilizing TEAMS, Zoom, etc.) and conducted by the grocery store nutritionists. Patient-preference for delivery (in-person vs. remote or a hybrid) of the Cooking Matters® grocery store tour will be considered to promote participation in the event that social distancing precautions remain in place or participants have transitioned to online grocery ordering. Share Our Strength's Cooking Matters® campaign is increasing efforts to deliver digital content through Zoom, Facebook Live, and YouTube and other platforms to support families with strategies and skills. The study team will collaborate with the in-store nutritionists across the region to utilize newly developed digital content to supplement in-store tour learning activities. Importantly, grocery store nutritionists have also started to transition to virtual care for their customers, thus a transition to digital delivery is consistent with their practice. Participants may receive educational materials by email or postal service mail, per participant preference. In an effort to best track completion of grocery store tours by Arm 3 participants, the study will implement a short Grocery Store Tour questionnaire for participants to complete. This 3-question questionnaire will ask the participant to report if they attended a tour, the grocery chain the tour occurred at, and whether the tour was in-person or online.

The active intervention in Arm 3 will last a total of 6 months with active participant involvement. Participant satisfaction will be collected following the first and last calls with the health coach. Following the 6-month intervention, follow-up measures will be collected at 6 months. For all arms, data will be extracted from the EHR during and following the 12-month period to assess the implementation and impact of the intervention on child BMI.

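### Switching provider is a ground for investigator withdrawal, and the plan does not say whether the child's later EHR BMI still enters the intention-to-treat analysis

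*Combined protocol and SAP*

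**What the plan says.** The Participant Withdrawal section of the combined protocol and SAP makes three statements that matter here.

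- For families who choose to withdraw: "Participants who choose to withdraw from the study will not be contacted for further survey data collection". Health-coach contact also stops in Arm 3.
- For withdrawal by the study: "Participants may be withdrawn from the study by an investigator if they choose to switch providers or leave Geisinger".
- For data: "All data collected up to the point of withdrawal may be used for analysis purposes".

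Other sections describe an outcome and an analysis that do not depend on staying with one PCP.

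- Outcomes, source: "BMI values will be obtained from Geisinger clinical care visits, documented in the EHR".
- Outcomes, timing: "values from baseline WCV to 9 to 18 month follow-up may be used to assess the primary outcome".
- Study Procedures: "For all arms, data will be extracted from the EHR during and following the 12-month period to assess the implementation and impact". The same section says that consent at enrolment covers extraction from the EHR as well as surveys.
- Analytic Plan, Aim 1: "all participants enrolled will be analyzed according to their group assignment at the point of care (WCV) regardless of intervention received and compliance".

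**The concern.** A change of PCP inside Geisinger does not remove the child from the source of the primary outcome. The next clinic visit is recorded in the same EHR, and a height and weight taken in the window would give a valid BMIz. Withdrawing that child serves no purpose for the primary analysis. Because the plan mentions only data obtained before withdrawal, the value may never be extracted, or two analysts may treat it differently.

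The timing adds to the problem. PCPs are the randomised units, and the baseline well child visit is where Arms 2 and 3 first differ from Arm 1. A later decision to leave that PCP comes after exposure and could depend on what the visit contained. If such children drop out of the outcome data, the missingness is avoidable and may be related both to arm and to weight trajectory. Intention to treat is meant to prevent this.

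It also works against the plan's own efforts. The Outcomes section adds parent-reported height and weight because clinical follow-up values were becoming harder to obtain. Setting aside a clinic-measured BMI while collecting a weaker substitute would be inconsistent.

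**Working it through.** **1. The plan's own figures**

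Inputs from Sample Size and Power: difference 0.05 BMIz, effect size 0.20, ICC 0.005, coefficient of variation 0.25, power 80%, alpha 0.025 per comparison, 20 PCPs per arm, 7% not receiving allocated treatment, 10% dropout. The Analytic Plan makes the test two-sided.

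- Individually randomised n per arm: 2 × ((2.241 + 0.842) / 0.20)² gives 476.
- Design effect at 28 families per PCP: 1 + ((1 + 0.25²) × 28 − 1) × 0.005 = 1.14375, and 476 × 1.14375 = 544.4. The smallest whole number per PCP that suffices with 20 PCPs is 28, so 20 × 28 = 560 per arm, as stated.
- Inflation: 560 / (1 − 0.17) = 674.7, so 675 per arm, as stated.
- Implied SD of BMIz change: 0.05 / 0.20 = 0.25.

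**2. The sections side by side**

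| Question | Participant Withdrawal | Study Procedures, Outcomes and Aim 1 analysis |
|---|---|---|
| Child changes PCP within Geisinger | May be withdrawn by an investigator | Still an enrolled participant, analysed whatever the compliance |
| BMI recorded after that change | Not mentioned; only data up to withdrawal are addressed | Obtainable from a Geisinger clinical visit, 9 to 18 months after baseline |
| EHR extraction after withdrawal | Not mentioned; survey and coach contact stop for those who choose to withdraw | Planned for all arms during and after the 12 months |

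No sentence settles the second and third rows for a withdrawn child.

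**3. Size of a possible bias**

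The documents give no switching rate, so both inputs below are assumptions. Let w be the excess proportion of children withdrawn in an intervention arm relative to Arm 1. Let d be how much more BMIz those children gain than the children who remain. If d is the same in both arms and nothing is imputed, the contrast shifts by about w × d.

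| w (assumed) | d (assumed) | Shift in BMIz | Share of the 0.05 target |
|---|---|---|---|
| 2% | 0.5 SD = 0.125 | 0.0025 | 5% |
| 2% | 1 SD = 0.25 | 0.005 | 10% |
| 5% | 0.5 SD = 0.125 | 0.00625 | 12.5% |
| 5% | 1 SD = 0.25 | 0.0125 | 25% |

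If the withdrawn children gain more, the intervention arm looks better than it is; if they gain less, the shift reverses. With no excess or no gap, the shift is zero.

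**4. Power**

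Intention to treat keeps the 7% group, so 10% dropout leaves 675 × 0.90 = 607.5 per arm. At 607.5 / 20 = 30.4 per PCP the design effect is about 1.156, the effective n about 525, and power about 84%. An assumed extra loss of 2%, 5% or 10% of enrolled children leaves 594, 574 or 540 per arm, with power of about 83%, 82% or 80%.

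**The case against.** The strongest reply is that the plan never says the later BMI is lost. The withdrawal text is permissive: a child may be withdrawn, and earlier data may be used. It does not bar later EHR values, and the contact it stops is surveys and coaching. Study Procedures and the Aim 1 analysis point towards keeping the value. This stands to the extent that loss of the endpoint is an inference. But the ordinary reading of a sentence that allows data up to withdrawal is that later data are not collected, and nothing in the plan overrides that reading.

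Other parts of the reply also carry weight.

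- **Blinding.** Research Design blinds the investigators, who hold the withdrawal discretion. A reader might infer that unblinded staff could withdraw children selectively, but the project manager and the research assistant are given no such authority. Blinding does not stop families' own switching from depending on arm.
- **The different-arm PCP text.** In Study Procedures, "the primary BMI outcome analysis is an intent- to-treat analyses and will include these children" concerns children whose baseline visit was conducted by a PCP in another arm. It does not address a later change of provider, so it should not be cited as a direct contradiction.
- **Stopping surveys.** A reader might infer that a parent who merely stops answering questionnaires falls under the withdrawal limit. The section covers those who choose to leave the study, and Missing Data Considerations treats questionnaire nonresponse as missing data.
- **Low expected switching.** Research Design expects most families to stay with the same PCP, and eligibility requires no plans to move or change health systems in 2 years. This suggests a small proportion but gives no figure.
- **Safeguards.** Reasons for loss are documented, participants with and without missing data are compared, and Appendix C compares attrition by arm. Random-forest imputation is planned depending on the amount missing. These reduce the harm, but imputing a value is a poor substitute for using one already in the record.

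**Conclusion.** The point holds as an unreconciled rule, and it should be corrected. Switching provider is a stated ground for investigator withdrawal, the plan is silent on EHR BMI afterwards, and the primary analysis is meant to include every enrolled child using an outcome that does not depend on the original PCP. The consequence is avoidable missingness that could differ by arm.

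The size is unknown. Under the assumed 2% to 5% excess and 0.5 to 1 SD gap, the shift is about 0.0025 to 0.0125 BMIz, or 5% to 25% of the 0.05 target. That range requires every excess switcher to be withdrawn, every later BMI to be set aside, and no recovery through imputation. A reader might take it as evidence of a material bias. The documents do not support that, because they report neither how often families switch nor how those children fare, and a full SD gap is at the severe end.

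The documents also do not support a claim that the trial becomes underpowered. A further loss of about 10% of enrolled children, on top of the planned 10% dropout, would be needed to bring power down to about 80%.

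**What to change.** In Participant Withdrawal, remove switching provider as a ground for investigator withdrawal. State that children who change PCP or clinic within Geisinger stay in the primary analysis in their assigned arm, with BMI extracted from the EHR in the 9 to 18 month outcome window.

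For participants who withdraw from surveys or coaching, record separately whether permission for EHR extraction is also withdrawn. Continue extraction unless it is, subject to the consent terms. Consent at enrolment covers extraction, but what it allows after withdrawal cannot be checked from the public documents and should be confirmed first. For families who leave Geisinger, later values may truly be unavailable; any in-window BMI recorded before they left can already be used under the current text.

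The cost is a wording amendment for the IRB and one extra field on the withdrawal log. The planned sample size does not change.
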